#### 4.4 Duration of Therapy

Treatment with AZD6244 will continue until the completion of chemoradiotherapy or until one of the following criteria applies:

- Toxicity requiring discontinuation (section 4.2)
- Disease progression,
- Intercurrent illness that prevents further administration of treatment,
- Unacceptable adverse event(s),
- Patient decides to withdraw from the study, or
- General or specific changes in the patient's condition render the patient unacceptable for further treatment in the judgment of the investigator.

In the event of a discontinuation of AZD6244 for a dose limiting toxicity the patient will continue to receive capecitabine and radiotherapy if not already completed.

#### 4.5 Duration of Follow Up

Patients will be followed for adverse events until three weeks after completion of chemoradiation. After this time they will be followed for the purpose of describing RTOG late toxicities until 36 months.

#### 4.6 Criteria for Removal from Study

Patients will be removed from study after follow up has been completed as in section 4.5 or if

- The patient refuses further follow up care at NIH

- General or specific changes in the patient's condition render the patient unacceptable for follow up in the judgment of the investigator
- Death.

The reason for study removal and the date the patient was removed must be documented in the Case Report Form.

## 5.0 DOSING DELAYS/DOSE MODIFICATIONS

### 5.1 AZD6244

AZD6244 dose reductions will occur in the event of a DLT. In the event of a DLT that is an overlapping toxicity with Capecitabine, AZD6244 will be dose reduced. If a Capecitabine associated toxicities occur following discontinuation of AZD6244, Capecitabine dose adjustments will occur as deemed appropriate by the Principal Investigator in conjunction with the participating Medical Oncology Associate Investigator. AZD6244 dose reductions will not occur for established non-DLT Capecitabine toxicities (e.g. Grade 2 hand-foot syndrome).

Dose de-escalation will occur as described in the table below for DLT's and the following overlapping toxicities

- **Grade  $\geq 3$  diarrhea that persists despite appropriate medical management including anti-diarrheal medications**
- **Grade  $\geq 3$  nausea and vomiting that persists despite appropriate medical management including anti-nausea medications**
- **Grade 2 hand foot that persists despite interruption of capecitabine**

Dose De-Escalation Schedule			
Dose Level	Dose		
	AZD6244	Capecitabine	Radiation*
Level -1	50 mg PO QD Weeks 1-7	825 mg/m  PO every 12 hours Weeks 2-7	5040 cGy Weeks 2-7
Level 1	50 mg PO BID Weeks 1-7	825 mg/m  PO every 12 hours Weeks 2-7	5040 cGy Weeks 2-7
Level 2	75 mg PO BID Weeks 1-7	825 mg/m  PO every 12 hours Weeks 2-7	5040 cGy Weeks 2-7
* An additional 360 cGy may be delivered for fixed T4 tumors for a total dose of 5400 cGy			

Diarrhea must be managed symptomatically. IV hydration and use of loperamide, as well as close observation, are recommended for diarrhea if clinically indicated. C If control takes

longer than 2 days, medical evaluation including relevant diagnostic procedures, alternative treatment, and possible investigation of DPD deficiency should be considered. Capecitabine and AZD6244 may be held for up to 72 hours and will not be re-started until diarrhea has resolved to grade  $\leq 1$ . In patients with grade 3 diarrhea evaluation for C. difficile colitis should be considered. Patients with neutropenia and diarrhea should be considered for empiric use of prophylactic antibiotics such as oral quinolones.

## 5.2 Capecitabine

Capecitabine will be withheld in cases of Grade 3 or greater neutropenia or Grade 2 or greater hand-foot syndrome or mucositis that do not respond to medical management. Capecitabine will be restarted after the symptoms improved to Grade 1. The dose of Capecitabine may be adjusted in the event of recurrent Grade 2 or greater hand-foot syndrome, neutropenia, or other Capecitabine toxicities that have not been attributed to AZD6244.

Summary of management of common Capecitabine toxicities during combined AZD6244 and Capecitabine dosing	
Toxicity	Capecitabine dose modification
Grade 2 hand foot syndrome	Interrupt until $\leq$ grade 1. May then restart capecitabine at full dose. For second occurrence, hold capecitabine until $\leq$ grade 1, then restart capecitabine one dose level lower (75% of starting dose first occurrence, 50% of the starting dose the second occurrence, discontinue the third occurrence).
Grade 3 hand foot syndrome	Interrupt until $\leq$ grade 1. Then restart capecitabine one dose level lower (75% of starting dose first occurrence, 50% of the starting dose the second occurrence, discontinue the third occurrence).
Grade 2 thrombocytopenia	Continue at current dose
Grade 3 thrombocytopenia	Hold until recovery until $\leq$ grade 1 then resume one dose level lower*
Grade 4 thrombocytopenia	Hold until recovery until $\leq$ grade 1 then resume one dose level lower*
Grade 3 neutropenia	Hold until recovery until $\leq$ grade 1 then resume one dose level lower*
Grade 4 neutropenia	Hold until recovery until $\leq$ grade 1 then resume one dose level lower*
$\geq$ Grade 3 febrile neutropenia	Hold until resolution of fever and neutropenia to $\leq$ grade 1. Then resume on dose level lower*
*Dose reductions for capecitabine 1. Starting dose 2. 75% of the starting dose 3. 50% of the starting dose	

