#### 4. Discontinuation of capecitabine.

### 5.3 Radiation

Radiation dose will not be adjusted based on toxicity. Delay in treatment may occur in the event that it is felt to be unsafe to deliver treatments due to the clinical status of the patient. Radiation treatment delays will be minimized as efficacy of radiotherapy is decreased with treatment delay. In the event that radiation is delayed for a toxicity, treatment with AZD6244 and capecitabine will be held until resumption of radiation. AZD6244 and capecitabine dose will be modified as described in section 5.1 and 5.2.

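### Section 5.2: the Grade 2 hand-foot row gives two capecitabine doses, 75% and 50% of the starting dose, for the same second event

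*Combined protocol and SAP*

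**What the plan says.** The starting dose of capecitabine is 825 mg/m2 every 12 hours on radiotherapy days (section 4.1.2). Section 5.2 tabulates what to do when common capecitabine toxicities occur.

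- **Grade 2 hand-foot syndrome, first event:** interrupt until Grade 1 or lower; "May then restart capecitabine at full dose".
- **Grade 2 hand-foot syndrome, second event:** "For second occurrence, hold capecitabine until" Grade 1 or lower, "then restart capecitabine one dose level lower (75% of starting dose first occurrence, 50% of the starting dose the second occurrence", and stop the drug at the third.
- **Grade 3 hand-foot syndrome:** interrupt until Grade 1 or lower, then one dose level lower from the first event on, with the same bracket.
- **Ladder under the table:** "Starting dose 2. 75% of the starting dose 3. 50% of the starting dose", and as step 4 "Discontinuation of capecitabine". In the available text, step 4 is printed just above section 5.3, but it belongs to this list.

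The rule is operative. Section 5.3 sends the reader to 5.1 and 5.2 for capecitabine dose changes when radiation is delayed for toxicity. Section 5.1 uses Grade 2 hand-foot syndrome as its example of a non-DLT capecitabine toxicity for which AZD6244 is not reduced, unless the event persists despite interrupting capecitabine. The capecitabine row is therefore the first line of control for this event.

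**The concern.** One sentence carries two instructions for the same event. Its main clause counts toxicity events and, starting from full dose, leads to 75%. Its bracket, if it counts the same thing, leads to 50%. The bracket also sits badly with the row's first event (75% against permitted full dose) and with the third (stop against 50%).

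The likely cause is that the bracket was written for the Grade 3 row, where the first event already triggers a reduction, and was carried unchanged into the Grade 2 row, where reduction starts one event later.

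What is at stake is uniform capecitabine dosing. Two clinicians applying the row in good faith could restart similar patients on different doses, or one could stop the drug where the other continues it. Section 7.4 says that adding AZD6244 may increase the side effects of capecitabine, so this is not a toxicity that the trial can set aside.

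**Working it through.** No sample size, error rate or other design figure is involved. The check sets the row against the ladder and then turns the two readings into doses.

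**Inputs.** Starting dose 825 mg/m2, twice daily (4.1.2). Ladder 100%, 75%, 50%, stop (5.2). Radiotherapy 25 fractions plus a 5.4 Gy boost in 1.8 Gy fractions (4.1.3.1). Rounding to the nearest 150 mg (4.1.2).

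**Two readings of the Grade 2 row**

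| Grade 2 event | Main clause and ladder | Bracket, counting events |
|---|---|---|
| 1st | 100% (permitted) | 75% |
| 2nd | 75% | 50% |
| 3rd | 50% | stop |
| 4th | stop | already stopped |

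If the bracket counts reductions, its first step falls at the second event and the right-hand column becomes the left-hand one. In the Grade 3 row the number of events and the number of reductions are the same, so that row raises no difficulty.

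The first-event line is permissive. A patient restarted at 75% after the first event would reach 50% at the second by the ladder as well, and there would be no conflict. The contradiction concerns the patient restarted at full dose, which is the only first-event dose that the row names.

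**Dose at the second event**

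- 75%: 0.75 × 825 = 618.75 mg/m2 per dose, or 1,237.5 per day.
- 50%: 0.50 × 825 = 412.5 mg/m2 per dose, or 825 per day.
- Gap: 618.75 − 412.5 = 206.25 mg/m2 per dose. This is 206.25 / 825 = 25% of the starting dose, and 206.25 / 618.75 = 33% below the higher reading.

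The documents give no body surface area. Assuming 1.5, 1.8 and 2.1 m2, and rounding to 150 mg, the choice per dose is 900 or 600 mg, 1,050 or 750 mg, and 1,350 or 900 mg. Rounding does not remove the difference.

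**Share of the course**

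- Treatment days: 25 + 5.4 / 1.8 = 28.
- Planned capecitabine: 28 × 2 × 825 = 46,200 mg/m2.
- Each day remaining after the second event: 2 × 206.25 = 412.5 mg/m2, and 412.5 / 46,200 = 0.9% of the plan.
- If 5 days remain: 5 × 412.5 = 2,062.5 mg/m2, or 4.5%.
- If 10 days remain: 10 × 412.5 = 4,125 mg/m2, or 8.9%.

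The 5 and 10 days are assumptions. The documents give no timing for capecitabine hand-foot syndrome.

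**The case against.** The strongest reply is that one reading is plainly best. Counting toxicity events makes the bracket disagree with the row it sits in at the first event, and at the second it drops a patient on full dose by two levels when the row says one. Counting successive reductions removes both conflicts and matches the ladder. The ladder's asterisk is attached to the blood-count rows, not the hand-foot rows, but the bracket uses the same steps and section 5.2 defines no other capecitabine dose level. This argument stands, and it settles what the fix should be. It does not make the row correct: the main clause has just used 'occurrence' for the toxicity event, and nothing tells the reader that the word changes meaning inside the bracket.

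The second reply is that the effect is small. A patient needs two Grade 2 events within about six weeks of capecitabine, in a trial of at most 18 patients (13.2), and the team meets weekly during active treatment to discuss each patient (6.8.1). That also stands. It makes divergent dosing less likely but does not correct the text.

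A reader might go further and see a second contradiction between the prose of 5.2 and its table. The prose says "Capecitabine will be restarted after the symptoms improved to Grade 1" and "The dose of Capecitabine may be adjusted in the event of recurrent Grade 2 or greater hand-foot syndrome, neutropenia", while the table orders a reduction after a first Grade 3 or 4 neutropenia or Grade 3 hand-foot event. The documents do not support calling this a conflict. The prose names no restart dose, so there are not two stated doses, and a general permission followed by a specific table is ordinary drafting.

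**Conclusion.** The Grade 2 hand-foot row is wrong as written, and the defect is minor. For a patient restarted at full dose, the second event literally yields 618.75 and 412.5 mg/m2 per dose, and the third yields 412.5 mg/m2 and discontinuation. Reading the bracket as a count of reductions resolves this in favour of 75% and then 50%, but the reader has to supply that meaning. The percentages follow from the protocol's own figures. The milligram doses and the share of the course rest on the assumed body surface area and remaining days.

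Three stronger inferences are not supported.

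- **That the trial's conclusions are affected.** Grade 2 hand-foot syndrome is not itself a DLT: the residual item in 4.2 starts at Grade 3. No DLT count, MTD rule or analysis uses the capecitabine restart dose.
- **That the problem will be frequent.** Section 6.2.1.2 gives single-agent Grade 3 or 4 rates (17% for hand-foot syndrome, 2.4% for neutrophils). Neither measures a second Grade 2 event, for which the documents give no rate.
- **That a large part of the course is at stake.** Having 20 of the 28 treatment days left after the second event would require two events and two holds within the first 8 treatment days, which is implausible. Third events have less time still.

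**What to change.** Reword the Grade 2 hand-foot row by event: first, full dose; second, 75% of the starting dose; third, 50%; fourth, discontinue. Alternatively, keep the sentence and replace 'occurrence' by 'reduction' inside the bracket. If the sponsor in fact intends 50% at the second event, the row should say so outright and drop the reference to a single dose level. The Grade 3 row can stay as it is.

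This is a change to the text of one table row. It alters no visit, assessment, sample size or analysis.

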#### 4. Discontinuation of capecitabine.

### 5.3 Radiation

Radiation dose will not be adjusted based on toxicity. Delay in treatment may occur in the event that it is felt to be unsafe to deliver treatments due to the clinical status of the patient. Radiation treatment delays will be minimized as efficacy of radiotherapy is decreased with treatment delay. In the event that radiation is delayed for a toxicity, treatment with AZD6244 and capecitabine will be held until resumption of radiation. AZD6244 and capecitabine dose will be modified as described in section 5.1 and 5.2.

## 6. ADVERSE EVENTS: LIST AND REPORTING REQUIREMENTS

Adverse event (AE) monitoring and reporting is a routine part of every clinical trial. The following list of AEs (Section 6.2) and the characteristics of an observed AE (Section 6.3) will determine whether the event requires expedited (via AdEERS) **in addition** to routine reporting.

### 6.1 Definitions

#### 6.1.1 Adverse Event

An adverse event is defined as any reaction, side effect, or untoward event that occurs during the course of the clinical trial associated with the use of a drug in humans, whether or not the event is considered related to the treatment or clinically significant. For this study, AEs will include events reported by the patient, as well as clinically significant abnormal findings on physical examination or laboratory evaluation. A new illness, symptom, sign or clinically significant laboratory abnormality or worsening of a pre-existing condition or abnormality is considered an AE. All AEs must be recorded on the AE case report form unless otherwise noted above in Section 6.1.

All AEs, including clinically significant abnormal findings on laboratory evaluations, regardless of severity, will be followed until satisfactory resolution. AEs should be reported up to 30 days following the last dose of study drug. AEs that are considered treatment related, expected, continuing, but not resolvable by 30 days after treatment completion (e.g., alopecia) will not be followed after the 30-day period.

An abnormal laboratory value will be considered an AE if the laboratory abnormality is characterized by any of the following:

- Results in discontinuation from the study
- Is associated with clinical signs or symptoms
- Requires treatment or any other therapeutic intervention
- Is associated with death or another serious adverse event, including hospitalization.
- Is judged by the Investigator to be of significant clinical impact
- If any abnormal laboratory result is considered clinically significant, the investigator will provide details about the action taken with respect to the test drug and about the patient's outcome.

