AZD6244 treatment and did not continue to rise beyond levels reached by the end of the first 4 weeks of treatment, except in patients at time points immediately prior to withdrawal due to disease progression. The majority of reported transaminase elevations either remained within normal limits or increased by no greater than 1 CTCAE grade. In Study D1532C00005 an increase in ALP was observed. However, no significant trends have been observed for bilirubin in any study, with either formulation. Regular measurements of AST, ALT and other liver function parameters will continue to be monitored and the health care professionals involved in clinical studies should look for signs of liver toxicity in patients receiving AZD6244. All patients with an aspartate aminotransferase (AST, SGOT), alanine aminotransferase (ALT, SGPT) or bilirubin value above upper limit of normal at the time of the last dose of AZD6244 should have a further liver chemistry profile (AST, ALT, bilirubin and alkaline phosphatase) performed 30 days after permanent discontinuation of AZD6244 in order to fully document reversibility.

In the melanoma Phase II study (D1532C00003) an increase in serum phosphate was observed in some patients after initiation of AZD6244 when compared with patients randomized to temozolomide. One patient on AZD6244 required therapeutic intervention initiated due to a calcium:phosphate product which exceeded 4.5 mmol/L. Regular monitoring of serum calcium and phosphorus levels, and the calcium:phosphate product is advised in clinical studies with AZD6244.

In Study D1532C00005, data shows a slight decrease in platelet count, however this was not considered clinically significant. No other clinically significant changes in hematological parameters were identified across the clinical study program. However, hematological events are potential risks, particularly when AZD6244 is administered in combination with other anti-cancer therapies.

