#### 6.2.1.2 Adverse Event List for Capecitabine

Capecitabine may cause diarrhea, sometimes severe. Standard anti-diarrheal treatments are recommended and dose reductions are employed for reoccurrence of grade 3 diarrhea. Grade 3 or 4 toxicities are described below for patients receiving Capecitabine as a single agent: diarrhea (12%), nausea (2%), stomatitis (2%), vomiting (2%), abdominal pain (3%), hand- and –foot syndrome (17%), decreased neutrophils/granulocytes (2.4%), hyperbilirubinemia (20%), decreased lymphocytes (13%). A comprehensive list of adverse events observed with Capecitabine can be found in the package insert. Diarrhea and rash are overlapping toxicities of AZD6244 and capecitabine and will be aggressively managed as per section 5.1.

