### 13. STATISTICAL CONSIDERATIONS

#### 13.1 Study Design/Endpoints

This is a Phase I trial in which patients will be treated with escalating doses of AZD6244. There will be no inpatient dose escalation. The primary endpoints will be the MTD and the DLT's. The dose-escalation will proceed in cohorts of 3-6 patients at each dose level. If 0/3 experience DLT, the next cohort starts one dose level higher. If 1/3 experience DLT, up to 3 more patients are started at that same dose level. If 2 or more experience DLT, no further patients are started at that dose. In the event that 2 or more patients of the first three enrolled at dose level 1 develop a DLT, de-escalation to dose level -1 will occur. The MTD or recommended Phase II dose is the dose level at which no more than 1 of 6 patients experience DLT during treatment and the three weeks after completion. Six additional patients will be treated at the recommended phase II dose in order to refine toxicity assessment and obtain reasonable amounts of biologic data.

The dose escalation will proceed only for AZD6244 while capecitabine and radiation doses remain constant. The schema for escalation is as follows:

Dose Escalation Schedule			
Dose Level	Dose		
	AZD6244	Capecitabine	Radiation*
Level -1	50 mg PO QD Weeks 1-7	825 mg/m  PO every 12 hours Weeks 2-7	5040 cGy Weeks 2-7
Level 1	50 mg PO BID Weeks 1-7	825 mg/m  PO every 12 hours Weeks 2-7	5040 cGy Weeks 2-7
Level 2	75 mg PO BID Weeks 1-7	825 mg/m  PO every 12 hours	5040 cGy Weeks 2-7

		Weeks 2-7	
* An additional 360 cGy may be delivered for fixed T4 tumors for a total dose of 5400 cGy			

Toxicity will be scored according to the CTCAE v4.0  
([http://ctep.cancer.gov/protocolDevelopment/electronic\\_applications/docs/ctcae4.pdf](http://ctep.cancer.gov/protocolDevelopment/electronic_applications/docs/ctcae4.pdf)).

Dose-limiting toxicities will be defined as follows (during treatment and within the first three weeks after treatment)

1. Recurring and persistent Grade 3 diarrhea despite appropriate medical therapy.
2. ANC <500 for more than 5 days or neutropenic fever
3. Grade 4 thrombocytopenia
4. Recurring and persistent Grade 3 nausea/vomiting despite appropriate anti-emetic therapy
5. Grade 4 dermatitis acneiform rash
6. Grade 4 fatigue
7. All other non-hematologic toxicities of grade 3 or higher except electrolyte abnormalities that are correctable

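### Section 6.1.1 does not use CTCAE grade to decide when a laboratory abnormality is an AE, so a toxicity profile built from the AE form can miss silent graded laboratory toxicity

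*Combined protocol and SAP*

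**What the plan says.** **AE definition (6.1.1).** The opening definition covers untoward events "whether or not the event is considered related to the treatment or clinically significant". The section then limits laboratory findings to clinically significant ones and sets a test: "An abnormal laboratory value will be considered an AE if the laboratory abnormality is characterized by any of the following". The alternatives are discontinuation from the study, signs or symptoms, treatment or other intervention, association with death or another SAE, and a discretionary one: "Is judged by the Investigator to be of significant clinical impact". The last bullet is a documentation instruction, not a criterion. On recording, the section says: "All AEs must be recorded on the AE case report form unless otherwise noted above in Section 6.1".

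**Toxicity and DLT (4.2, 13.1).** Section 13.1 states: "Toxicity will be scored according to the CTCAE v4.0". Three DLT items can be met by a laboratory value:
- item 2: ANC below 500 lasting over 5 days (or neutropenic fever);
- item 3: Grade 4 thrombocytopenia;
- item 7: "All other non-hematologic toxicities of grade 3 or higher except electrolyte abnormalities that are correctable".

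Section 13.1 also requires at least possible attribution to the study treatment. None of the three items asks for symptoms or treatment of a laboratory value.

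**Objective and data.** Section 1.1 makes the DLTs and the toxicity profile a primary objective. Section 10 schedules CBC with differential and serum chemistry (including bilirubin, AST and ALT) weekly in weeks 1 to 9 and again at week 11. Section 13.1 does not say whether the laboratory part of the profile comes from these results or from the AE form.

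**The concern.** Section 6.1.1 selects laboratory values by consequence or judgement, while 13.1 scores toxicity by grade. Where the two differ, the laboratory part of the toxicity profile depends on whether an investigator regarded a value as important. Two patients with identical results could appear differently in the table. The error runs one way: silent laboratory toxicity is left out and the combination looks cleaner than it was.

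The protocol itself expects laboratory effects. Section 6.2.1.2 gives Grade 3 or 4 hyperbilirubinemia in 20% of patients on single-agent capecitabine. Section 2.1.2.2 describes mean ALT and AST increases within a week of starting AZD6244. Section 6.2.1.1 lists ALT, AST, alkaline phosphatase and platelet changes as possibly related to the agent.

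**Working it through.** The plan states no figure on this point. The main check is therefore a comparison of text, and the arithmetic only illustrates size.

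**1. Individual records put through both rules**
- *Grade 3 ALT or bilirubin in one weekly sample; no symptoms, no treatment, patient stays on study.* Under 6.1.1 it is an AE only through investigator judgement. Under 4.2/13.1 it is a DLT by item 7 if at least possibly attributable. The capecitabine table in 5.2 has no hepatic row, so that table does not force an action that would bring the value within 6.1.1.
- *Grade 2 ALT over several samples.* It is not a DLT. It carries a CTCAE grade, but nothing in 6.1.1 requires an AE entry unless the investigator judges it important.
- *Grade 3 thrombocytopenia, Grade 3 neutropenia without fever, or a correctable electrolyte abnormality.* None is a DLT under 4.2, so the mismatch on DLT concerns items 2, 3 and 7 only.

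**2. Does the AE filter reach the DLT count?** No section says that a DLT must first be a 6.1.1 AE. Several sections nevertheless run along the AE route. Section 4.2 refers to its DLT items as adverse events. The only attribution scale, in 6.3, is written for AEs. Sections 4.5 and 6.4.3 end AE follow-up three weeks after chemoradiation, where the DLT window also closes. In 6.8.1 the principal investigator reviews adverse event and response data, but the same section bases escalation on toxicity data, which is wider.

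**3. Events at stake in the profile.** Input from 13.3: 12 patients at the MTD. Assumed: a silent Grade 3 or higher non-hematologic laboratory event with probability l per patient. Expected number = 12l; chance of at least one = 1 − (1 − l)^12.

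| l (assumed) | Expected in 12 | At least one in 12 |
|---|---|---|
| 5% | 0.6 | 0.46 |
| 10% | 1.2 | 0.72 |
| 20% | 2.4 | 0.93 |

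These are ceilings on what could be omitted, since an investigator may still record the events.

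**4. Illustration: what would follow if DLTs were read from the AE form.** A level clears the 3+3 with 0 of 3, or with 1 of 3 and then 0 of 3:

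P(clear) = (1 − p)^3 + 3p(1 − p)^2 × (1 − p)^3

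Let d be the assumed rate of all other DLTs. If silent events are dropped, p = d. If they are counted and independent, p = 1 − (1 − d)(1 − l). For d = 10% with silent events dropped, 0.729 + 0.243 × 0.729 = 0.906. For d = 10% and l = 10%, p = 0.190 and P(clear) = 0.730.

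| d | Dropped | Counted, l = 5% | l = 10% | l = 20% |
|---|---|---|---|---|
| 10% | 0.906 | 0.824 | 0.730 | 0.536 |
| 20% | 0.709 | 0.622 | 0.536 | 0.378 |
| 30% | 0.494 | 0.425 | 0.360 | 0.248 |

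At d = 10% the differences are about 8, 18 and 37 percentage points. They depend on the assumed rates and on a data path that the documents do not prescribe.

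**The case against.** A reader might infer that the DLT count itself omits these events and that the 3+3 therefore escalates too readily. The documents do not support that. Sections 4.2 and 13.1 define DLT on toxicities, escalation in 6.8.1 rests on toxicity data discussed by the team each week, and the laboratory results are available weekly during treatment. A recognised DLT also calls for an AZD6244 dose reduction under 5.1. For Grade 4 platelets, 5.2 requires a capecitabine change as well. An investigator who has just changed dosing because of a value could hardly say that it lacked clinical impact. This part of the objection stands.

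Two other overstatements should be avoided. Section 6.1.1 does not require a clinical consequence in every case, because the judgement criterion needs neither symptoms nor treatment. DLT is not decided by grade alone either: attribution applies throughout, items 1 and 4 require persistence despite therapy, item 2 has a duration, and item 8 is a radiation delay.

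The rates are also open to challenge. The 20% is all Grade 3 or 4 hyperbilirubinemia on single-agent capecitabine, not silent events on this regimen. Section 2.2 names diarrhea, in up to 20%, as the most common Grade 3 or higher toxicity of capecitabine in this setting, so 20% for silent bilirubin events is an extreme bound. Section 3.1.5 requires normal bilirubin at entry (Gilbert's excepted), and 2.1.2.2 reports no significant bilirubin trend with AZD6244. On transaminases, 2.1.2.2 says: "The majority of reported transaminase elevations either remained within normal limits or increased by no greater than 1 CTCAE grade". That makes Grade 3 events less likely.

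None of this closes the gap in the profile. Silent low-grade rises are what the 6.1.1 list lets through unrecorded, and a silent Grade 3 value reaches the AE form only if someone judges it important or recognises it as a DLT.

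**Conclusion.** The point holds for the toxicity profile. Section 6.1.1 conflicts with its own opening and does not match the laboratory DLT items. A profile compiled from the AE form can therefore omit asymptomatic, untreated graded laboratory toxicity. The documents do not fix how much: 0.6 to 2.4 Grade 3 or higher events among 12 patients is a ceiling under assumed rates of 5% to 20%, with the upper end unlikely.

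For the DLT count the finding is limited to an operational risk, which arises only if DLTs are taken from AE entries. The 3+3 clearance probabilities show why that path should be closed; they are not an effect of the text. The change is a cheap improvement. The escalation rule itself is not at fault.

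**What to change.** - **6.1.1:** state that any laboratory value that meets a DLT item in 4.2, or is CTCAE Grade 3 or higher, is recorded as an AE whether or not it meets the existing list.
- **13.1:** state that the laboratory part of the toxicity profile is the worst CTCAE v4.0 grade per patient, and that the laboratory elements of DLT items 2, 3 and 7 are assessed from the CBC and chemistry results scheduled in section 10. Include any unscheduled repeats, because weekly samples alone cannot time the duration in item 2.

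The attribution rule, the correctable-electrolyte exception and all dose-modification rules stay as they are.

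The cost is two sentences, one tabulation from data already collected, a few more AE entries and a slightly less favourable toxicity table. Values that become AEs also fall under the expedited-reporting table in 6.4.2, so the sponsor should check which laboratory terms are exempt.
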